BMBC	Bone Marrow Blast Count
BMI	Body Mass Index
C	Course
CR	Complete Remission
CRi	Complete Remission with incomplete recovery
CRF	Case Report Form
CRO	Contract Research Organization
D	Day
dps	decimal places
DSMB	Data Safety Monitoring Board
ECOG	Eastern Cooperative Oncology Group
EORTC	European Organization for Research and Treatment of Cancer
HLT	High Level Terms
HLGT	High Level Group Terms
ICH	International Conference on Harmonisation
ICTA	International Clinical Trial Association
ITT	Intention To Treat
IU	International Unit
IWRS	Interactive Web Response Services
LDAC	Low dose cytarabine
LLT	Lowest Level Terms
LOCF	Last Observation Carried Forward
MEDDRA	Medical Dictionary for Regulatory Activities
mRNA	Messenger Ribonucleic Acid
FAS	Full Analysis Set
FPFV	First Patient First Visit
LDAC	Low Dose Cytarabine
LPLV	Last Patient Last Visit
NCI CTCAE	National Cancer Institute Common Terminology Criteria for Adverse Events
PFS	Progression Free Survival
PBBC	Peripheral Blood Blast Count

Abbreviation	Definition
PP	Per Protocol
PD	Progressive Disease
PR	Partial Remission
PT	Preferred Term
QOL	Quality Of Life
RBC	Red Blood Cells
SAP	Statistical Analysis Plan
SAS	Statistical Analysis Software
SOC	System Organ Class
SOP	Standard Operating Procedure
TFL	Tables Figures Listings
WHO	World Health Organization

1. INTRODUCTION

The Statistical Analysis Plan (SAP) details the statistical methodology to be used in analyzing study data and outlines the statistical programming specifications, tables, figures and listings. It describes the planned analyses of the data collected during the study, including the safety and efficacy variables and populations, anticipated data transformations and manipulations, and other details of the analyses not provided in the study protocol, for the purpose of submission to the relevant authorities and for publication as appropriate. The results of all analyses in this SAP will be included in the Clinical Study Report (CSR).

This SAP is based on the following study documents:

- Protocol Version 7 dated 05OCT2015
- Protocol Amendment n°4 dated 05OCT2015
- Electronic Case Report Form (eCRF) for the study.

The statistical analyses will be performed in accordance with International Conference on Harmonization (ICH) E9 guidelines. This SAP conforms to the Cytel standard operating procedure STAT C002 Timing and Content of Statistical Analysis Plans.

The SAP should be validated and signed before the study database is locked.

Specifications of outputs (i.e. TLFs shells) will be described in a separate document.

The primary analyses were to be undertaken when all enrolled patients had completed treatment and follow-up period for 2 years. However, based on the outcome of the AML Advisory Board meeting conducted on 24th January 2017, there was a consensus that the study was not adequately powered for the key endpoint of overall survival (OS) and that the purpose of the statistical analyses was therefore to identify a signal strong enough to support proceeding to phase 3.

This is a phase 2 proof of concept study and all efficacy parameters will be considered as the basis for conclusions regarding the activity of GRASPA in this population. P-values will be calculated for analyses of the primary endpoints in all patients. A two-sided 0.05 level of significance will be used as a guidance for interpretation of the data, but strict statistical significance will not be the only basis on which efficacy will be judged. In particular, the conclusions will not be based solely on the primary analysis of the primary endpoint. As indicated at the advisory board meeting, a Hazard Ratio (HR) less than 0.8 would indicate an interesting level of activity (approximately an increase in median OS from 6.4months to 8.0 months), which would warrant further investigation in a Phase 3. The activity of GRASPA will be concluded collectively in relation to the clinical relevance as indicated by the magnitude of effect across a range of endpoints (the totality of evidence).

2. OBJECTIVES OF STATISTICAL ANALYSIS

This statistical analysis plan (SAP) is designed to outline the methods to be used in the analysis of study data in order to answer the study objective(s). Populations for analysis, data handling rules, statistical methods, and formats for data presentation are provided. The statistical analyses and summary tabulations described in this SAP will provide the basis for the results sections of the clinical study report (CSR) for this trial.

This SAP also will outline any differences in the currently planned analytical objectives relative to those planned in the study protocol.

2.1.1. Primary objective

The primary objective is to evaluate Overall Survival (OS) in AML patients 65 to 85 years unfit for intensive chemotherapy, when treated with GRASPA plus low-dose cytarabine (LDAC) compared to low-dose cytarabine alone (LDAC).

2.1.2. Secondary and exploratory objectives

[figure not shown]
The secondary and exploratory objectives are to evaluate:

- Response to treatment
- Progression Free Survival (PFS)
- Relapse Free Survival
- Patient transfusion needs
- Patients' quality of life evolution
- Number of hospitalizations
- Safety of GRASPA in combination with cytarabine
- Pharmacokinetic and pharmacodynamic parameters of GRASPA®
- Immunogenicity of GRASPA
- Asparagine Synthetase (ASNS) expression and sensitivity to L-asparaginase in bone marrow cells (optional)
- Biomarker cytogenetic testing (optional)

3. STUDY DESIGN

3.1. Synopsis of Study Design

This is a multicentre, open label, randomized 1:2 (control versus GRASPA), controlled phase IIb trial in Europe, evaluating efficacy and tolerability of GRASPA. The trial follows the scheme below:

In both treatment and control arms, patients will be treated with subcutaneous LDAC as 40 mg daily (either one single dose of 40 mg or 20 mg twice daily according to local practice) for 10 consecutive days per course, each course occurring every 28 days \pm 3 days, for a duration up to 24 months. Each period of 28 days constitutes a cycle of chemotherapy. The dosage could be adjusted to 20 mg once daily in case of toxicities; a higher dose is also acceptable if required by the patient's status, at the investigator's decision.

In the experimental group, the patients will receive subcutaneous LDAC, as described above, and GRASPA (100 U/kg) given as an intravenous infusion at Day 11 of each 28 day course.

Patients will be required to attend a visit once a month, as the course begins.

When study treatment is stopped (main expected reasons are limiting toxicity, PD, or no evidence of treatment benefit), the visits will take place every 3 months until 24-months study duration has been reached.

An Independent Data Monitoring Committee (IDMC) was set-up for regular data reviews for safety: they reviewed the tolerance of GRASPA when 30 patients had been enrolled, to evaluate limiting toxicities defined as one of the following:

- grade 3 or 4 pancreatic toxicity
- grade 3 or 4 hepatic toxicity, allergic reaction, or coagulation event

- other non-hematologic grade 4 toxicity or requiring treatment change at investigator's decision

Specific attention is paid on type II diabetic patients treated with oral hypoglycemic agents for their diabetes, randomized to LDC + GRASPA.

The IDMC also reviewed safety and tolerance of GRASPA when 60 patients had been enrolled, at the end of recruitment and when 60 PFS events had been observed.

Additional information is provided in the IDMC Charter and the minutes of the IDMC meetings.

3.2. Randomization Methodology

The patients will be randomly and sequentially allocated to either one of the two treatments A or B, and the treatment allocation will be stratified by Eastern Cooperative Oncology Group (ECOG) performance status (PS=0 or 1 versus PS=2). This will ensure balance between the performance groups, which was been identified as a risk factor for early death.

Randomization 1:2 will be performed using Interactive Web Response Services (IWRS).

Randomization group will be confirmed to investigator by e-mail, specifying the treatment arm assigned, namely A or B, as follows:

- A: Low-dose cytarabine
- B: Low-dose cytarabine + GRASPA

Randomization will continue until 123 patients are recruited and receive study treatment.

3.3. Stopping Rules and Unblinding

An interim analysis was originally planned to be performed when half of the 123 expected PFS events had occurred (i.e. 60). The study could have been stopped at this point for futility. However, this interim analysis was not undertaken.

3.4. Study Procedures

The schedule of assessments, as outlined in the study protocol, is provided in Table 1.

Table 1: Schedule of Assessments

Day	D – 28 max.	TREATMENT COURSE – 28 days cycle (+/- 3 days)													
		1	2	3	4	5	6	7	8	9	10	11	13	18	23
Visit	Inclusion	1/2/3 ...													
Consent	X														
Demographics	X														
Inclusion/exclusion criteria	X														
Medical history	X														
AML history/ assessment (a)	X														X*
Clinical assessment (b)		X													
Quality of life survey		X													
Randomization	X														
Low-dose cytarabine		X	X	X	X	X	X	X	X	X	X				
GRASPA										P		X			
IAST (c)										X					
PK- PD (only for GRASPA receiving patients) (d)											X	X	X		X
Immunogenicity (only before GRASPA administration)											X				
Biology (e)	X	X (f)			X			X			X	X	X	X	X
Patient diary distribution and/or review		X													

(a) Bone marrow aspiration and extramedullary assessment may take place in the 4 weeks prior to randomization, for baseline status; samples for biomarkers assessments should be sent within max. 2 days after collection;

(b) including occurrence of AE/SAE; concomitant treatment;
(c) Irregular Antibodies Screening Test only for patients receiving GRASPA;
(d) See PK-PD assessments table 5
(e) hematology (CBC) ; biochemistry ; coagulation parameters; serology tests only at inclusion; pregnancy test at inclusion and end of treatment, if applicable
(f) for the first course = if biochemistry/hematology tests are available within 7 days, it is not necessary to repeat them; for coagulation tests – results should not be older than 3 days; for subsequent courses = to be performed within max. 3 days before next treatment course start;
P : prescription of GRASPA;

*: before the next treatment course

Table 2: Calendar of Study PK/PD Assessments

Table 3: Calendar of Study Assessments – Follow-Up

Visit	End of treatment	every 3 Months until M24 (M3, ...)* +/- 2 weeks
AML assessment	X	X
Clinical assessment, including Adverse events review and assessment and Concomitant medications	X	X
Quality of life survey	X	X
Subsequent AML therapy	X	X
Patient diary return and review	X	

*: a phone call, at minimum, will be performed at 4 months (+/- 1 week) after end of study treatment, for safety assessment
Patient will have to attend visit every 28 days (+/- 3 days), at the start of each cycle, for a duration up to 24 months. Assessments required are provided in Tables 1 and 2.

When study treatment is stopped (see required conditions in section 8.9), the visits will take place every 3 months until 24-months study duration.

3.5. Efficacy, Pharmacokinetic, and Safety Variables

3.5.1. Efficacy Variables

The primary objective of this study is to evaluate the efficacy and tolerability of GRASPA when combined with LDAC. The primary endpoint is overall survival (OS), defined as the time elapsed between randomization and death for any cause. Patients not known to have this event are censored on the date they were last examined.

Secondary efficacy endpoints include the following:

- 1) Complete remission (CR), Complete remission with incomplete recovery (neutrophil or platelet regeneration, CRI), Partial remission (PR)
- 2) Progression-free survival (PFS) defined as the time elapsed between randomization and resistant disease or relapse or death from any cause
- 3) Relapse Free Survival defined only for patients who achieved CR or CRI as the time elapsed between date of CR/CRI and date of disease relapse or death from any cause
- 4) Percentage of patients who need transfusions (red blood cells and/or platelets), number of transfusions by patient
- 5) Patient quality of life evaluated using the EORTC QLQ-C30 version 3 scale
- 6) Number of hospitalizations (except scheduled protocol visit) required during the study

3.5.2. Pharmacokinetic Variables

Blood samples for determination of GRASPA pharmacokinetics were to be collected as outlined in the protocol. Pharmacokinetic parameters to be determined include minimum plasma concentration (C_{min}), maximum plasma concentration (C_{max}), time to maximum plasma concentration (T_{max}), the distribution rate constant (λ_{z1}), distribution half-life (dist $t_{1/2}$), elimination rate constant (λ_{z2}), terminal elimination half-life (elim $t_{1/2}$), area under the concentration versus time curve (AUC), clearance (Cl/F), and volume of distribution (β) ($Vd_{\beta/F}$).

Pharmacokinetic and pharmacodynamic endpoints include the following:

- 1) Plasma concentrations of asparagine, aspartate, glutamine, glutamate
- 2) Whole Blood L-asparaginase activity
- 3) Immunogenicity by measuring titer of anti-L-asparaginase antibodies
- 4) Biomarker cytogenetic testing (optional)
- 5) Measurement of the following parameters on harvested bone marrow tumor cells (optional):
 - a. Asparagine synthetase protein expression
 - b. Asparagine synthetase mRNA expression

c. In vitro sensitivity to L-asparaginase

3.5.3. Safety Variables

All subjects who received at least one dose of investigational products will be included in the safety analyses. Safety data will be summarized using actual treatment received, regardless of randomized treatment.

Safety and tolerability will be assessed in terms of AEs, SAEs, laboratory data and vital signs which will be collected for all subjects. AEs will be coded according to the Medical dictionary for regulatory activities (MedDRA) version 15.1 or higher. The intensity of AEs will be graded according to the NCI-CTCAE (version 4.0).

AEs, AE leading to study treatment discontinuation, AE related to study treatment, and SAEs will be listed individually by subject, and summarized by System Organ Class (SOC) and Preferred Term (PT) by treatment group. Summary of AEs with NCI-CTCAE grade 3 or 4 and most frequent PT will also be provided.

Specific attention will be given to NCI-CTCAE Grade 3 or 4 of pancreatic toxicity, Grade 3 or 4 of hepatotoxicity, allergic reactions or coagulation disorders, known to be potentially related to L-asparaginase as well as to hypoproteinemia and hyperglycemia/diabetes events.

Specific safety endpoints will include the following:

- 1) Safety of GRASPA in combination with low-dose cytarabine, with specific attention to :
 - a. Grade 3 or 4 of pancreatic toxicity
 - b. Grade 3 or 4 of hepatic toxicity, allergic reaction or coagulation event
 - c. Grade 3 or 4 of hypoproteinemia or hyperglycemia/diabetes
 - d. All other non-hematologic Grade 4 toxicities

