4.3.2 Secondary endpoints

- Percentage of patients with Complete remission (CR), Complete remission with incomplete recovery (neutrophil or platelet regeneration, CRi), Partial remission (PR)
- Progression-free survival (PFS) defined as the time elapsed between randomization and resistant disease or relapse or death from any cause
- Relapse Free Survival defined only for patients who achieved CR or CRi as the time elapsed between date of CR/CRi and date of disease relapse or death from any cause
- Percentage of patients who need transfusions (red blood cells and/or platelets), number of transfusions by patient
- Patient quality of life evaluated using the EORTC QLQ-C30 version 3 scale
- Number of hospitalizations (except scheduled protocol visit) required during the study
- Safety of GRASPA in combination with low-dose cytarabine, with specific attention to :
 - o Grade 3 or 4 of Pancreatic toxicity
 - o Grade 3 or 4 of hepatic toxicity, allergic reaction or coagulation event
 - o Grade 3 or 4 of hypoproteinemia or hyperglycemia/diabetes
 - All other non-hematologic Grade 4 toxicities

(*NB* grading reference used: NCI CTCAE version 4.0)

- Pharmacokinetic and pharmacodynamic parameters:
 - o Plasma concentrations of asparagine, aspartate, glutamine, glutamate
 - Whole Blood L-asparaginase activity
- Immunogenicity by measuring titer of anti-L-asparaginase antibodies
- Biomarker cytogenetic testing (optional)
- Measurement of the following parameters on harvested bone marrow tumor cells (optional):
 - Asparagine synthetase protein expression
 - Asparagine synthetase mRNA expression
 - In vitro sensitivity to L-asparaginase

(See also section 8.8 for details)

Table 3 hereafter provides the definitions of response criteria in AML.

Category	Definition
Complete remission (CR)*	Bone marrow blasts < 5%; absence of blasts with Auer rods; absence of extramedullary disease; absolute neutrophil count > $1.0 \times 10^{9}/L$ (1000/µL); platelet count > $100 \times 10^{9}/L$ (100 000/µL); red blood cell transfusion independence
CR with incomplete recovery (CRi)	All CR criteria except for residual neutropenia ($< 1.0 \times 10^{9}/L [1000/\mu L]$) or thrombocytopenia ($< 100 \times 10^{9}/L [100 000/\mu L]$)
Partial remission (PR)	all hematologic criteria of CR; decrease of bone marrow blast percentage to 5% to 25%; and decrease of pre-treatment bone marrow blast percentage by at least 50%

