8.11 End of study treatment

Patients will stop study treatment in following situations:

- Disease relapse or presence of a resistant disease, unless the investigator considers that the patient has a clinical benefit from continuing the treatment. In this case, the investigator should continue to perform the same study visits as long as considered clinical beneficial.
- Occurrence of GRASPA-related toxicity, such as:
 - Grade 3 or 4 pancreatic toxicity
 - o Grade 3 or 4 hepatic toxicity, allergic reaction, or coagulation event
 - o other non-hematologic Grade 4 toxicity

Patient assessment should continue as planned until evidence of relapse or presence of a resistant disease, in which case, patient will be followed up for survival.

- Patient unwilling to continue
- No evidence of study treatment benefit at investigator's decision

9. Investigational product: GRASPA

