11.6 Independent Data Monitoring Committee

An Independent Data Monitoring Committee (IDMC) will review the safety and tolerability of GRASPA at the following time points:

- when 30 patients have been enrolled, to evaluate limiting toxicities as defined in stopping rules,
- when 60 patients have been enrolled.

The original remit of the IDMC was to review the efficacy of GRASPA following 60 PFS events. The IDMC meeting will still take place following the accrual of these events, but with remit of safety review only. Thereafter, the IDMC will convene every 6 months for safety review

Specific attention will be paid on patients with type II diabetes treated with oral hypoglycemic agents: IDMC will assess 5 first of those patients enrolled after at least one month follow-up, and may reconsider study enrollment of such patients.

To avoid any conflict between the evaluation of safety and the primary efficacy endpoint OS, deaths in the study will be presented to the IDMC only in terms of overall frequencies and individual patient narratives. In particular Kaplan-Meier curves and p-value comparisons of those curves will not be presented.

The IDMC will work completely independently of the sponsor. Sponsor representatives will not attend those meetings of the IDMC where study data aggregated by treatment group will be considered. A specific document will be edited separately providing IDMC members details and conditions for such evaluation during IDMC meetings.

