5.8.1. Adverse Events

Safety and tolerability will be assessed in terms of AEs, SAEs, laboratory data and vital signs, which will be collected for all subjects. The AE term (Investigator term) will be assigned to the lowest level term (LLT), and a preferred term (PT) will be classified by a high level term (HLT), a high level group term (HLGT) and a system organ class (SOC) according to the Medical Dictionary for Regulatory Activities (MedDRA) thesaurus, Version 15.1 or higher depending on the latest version available during the study. The intensity of AEs will be graded according to the NCI-CTCAE (version 4.0).

An overview of the number of patients with AEs and the corresponding number of AEs will be presented through tables and listings:

- Total AE count
- Any AE
- Any treatment-related AE (Cytarabine and/or GRASPA®)
- Any AE of CTCAE grade ≥ 3
- Any AE of CTCAE grade = 4
- Any treatment-related (Cytarabine and/or GRASPA®) AE of CTCAE grade ≥ 3
- Any severe treatment-related (Cytarabine and/or GRASPA®) AE
- Any AE with outcome of death
- Any serious AE

- Any treatment-related (Cytarabine and/or GRASPA®) serious AE
- Any AE leading to permanent discontinuation
- Any treatment-related (Cytarabine and/or GRASPA®) AE leading to permanent discontinuation (Action taken=Withdrawn)
- Any AE leading to temporary discontinuation
- Any treatment-related (Cytarabine and/or GRASPA®) AE leading to temporary discontinuation (Action taken=Reduced)

An AE will be considered as “treatment-related” if the relationship to study treatment is ticked “possible,” “probable” or “certain/definite”.

For subject counts, subjects are included only once, even if they experienced multiple events in that category.

All the following summaries will be displayed by treatment groups on the safety population:

- All AE by System Organ Class (SOC) term, Preferred Term (PT)
- AE Experienced by $\geq 5\%$ of Subjects by SOC term and PT
- Treatment-related (Cytarabine and/or GRASPA®) AE by SOC term and PT
- AE of CTCAE grade ≥ 3 by SOC term and PT
- AE of CTCAE grade = 4 by SOC term and PT
- Treatment-related (Cytarabine and/or GRASPA®) AE of CTCAE grade ≥ 3 by SOC term and PT
- Severe treatment-related (Cytarabine and/or GRASPA®) AE by SOC term and PT
- AE with outcome of death
- Serious AE
- Treatment-related (Cytarabine and/or GRASPA®) serious AE
- AE leading to permanent discontinuation
- AE leading to temporary discontinuation

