14.3.1.2.6	Incidence of Treatment Related Treatment Emergent Serious Adverse Events by Preferred Term	Safety
14.3.1.2.7	Incidence of Treatment Emergent Adverse Events of Special Interest by Preferred Term	Safety
14.3.1.2.8	Incidence of Treatment Emergent Adverse Events of Special Interest with Toxicity Grade of 3 or 4 by Preferred Term	Safety
14.3.1.2.9	Incidence of Treatment Emergent Adverse Events Occurring in at least 5% of Patients in either Treatment Group by MedDRA Preferred Term	Safety
14.3.1.3	Listing of Treatment Emergent Adverse Events Leading to Either GRASPA or Chemotherapy Withdrawal	Safety

Table/Figure Number	Output Title	Analysis Set
	Deaths	
14.3.2.1	Deaths and Deaths within 28 Days After Last IMP Administration	Safety
14.3.2.2	Listing of All Deaths	Safety
	Clinical Laboratory Data	
	Biochemistry	
14.3.3.1.1	Biochemistry – Summary of Shift From Baseline to Worst Post-Baseline Results	
14.3.3.1.2	Biochemistry – Summary Statistics for Clinically Significant Parameters by Treatment Group and Time	
	Hematology	
14.3.3.2.1	Hematology – Summary of Shift From Baseline to Worst Post-Baseline Results	Safety
14.3.3.2.2	Hematology – Summary Statistics for Clinically Significant Parameters by Treatment Group and Time	Safety
	Coagulation	
14.3.3.3.1	Coagulation – Summary of Shift From Baseline to Worst Post-Baseline Results	Safety

Table/Figure Number	Output Title	Analysis Set
14.3.3.3.2	Coagulation – Summary Statistics for Clinically Significant Parameters by Treatment Group and Time	Safety
	Other Safety Parameters	
	Vital Signs Data	
14.3.4.1.1	Vital Signs – Descriptive Statistics for Change From Baseline	Safety
14.3.4.1.2	Vital Signs – Listing of Clinically Significant Values	Safety
14.3.4.2	ECOG Performance Status – Shift From Baseline to Worst Post-Baseline Value	Safety

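### The named severe-toxicity endpoints, three adverse-event tables and the maximum-grade rows stop at Grade 4, so the severe special-interest comparison by arm leaves out fatal (Grade 5) events, which are reported only elsewhere

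*SAP*

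**What the plan says.** **Grading.** Protocol 11.1.2.3 adopts CTCAE version 4.0. For terms outside it, the section gives its own scale, in which fatal is a separate Grade 5. The SAE form in protocol Appendix 7 also lists death as Grade 5, and protocol 11.1.2.5 requires every fatal AE to be declared as an SAE.

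**Named endpoints.** SAP 3.5.3 lists "Grade 3 or 4 of pancreatic toxicity" and "Grade 3 or 4 of hepatic toxicity, allergic reaction or coagulation event", applies the same limit to hypoproteinemia and hyperglycemia/diabetes, and restricts all remaining non-hematologic toxicity to Grade 4. Protocol 4.3.2 has the same limits, ending with "All other non-hematologic Grade 4 toxicities".

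**Analyses.** SAP 5.8.1 plans overall and SOC/PT summaries without an upper limit ("Any AE of CTCAE grade ≥ 3") and a summary of AEs ending in death. Its shell for diabetogenic and pancreatic events has rows for fatal events, but the maximum-grade block ends at Grade 4.

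**Outputs.** In SAP 8.1, Tables 14.3.1.2.3 and 14.3.1.2.4 are restricted to Grade 3 or 4. So is Table 14.3.1.2.8: "Incidence of Treatment Emergent Adverse Events of Special Interest with Toxicity Grade of 3 or 4 by Preferred Term". Table 14.3.1.2.7 covers special-interest events at all grades.

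**Limiting toxicity.** SAP 3.1 ends its list with "other non-hematologic grade 4 toxicity or requiring treatment change at investigator's decision". Protocol 8.11 has "Occurrence of GRASPA-related toxicity, such as" as a reason to stop treatment. Protocol 11.6 asks the IDMC "to evaluate limiting toxicities as defined in stopping rules".

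**The concern.** A severe-toxicity endpoint should count the worst grade. With the limit at Grade 4, an event that would have counted had the patient survived stops counting because the patient died. The loss also need not be equal across arms. If a larger share of severe events is fatal in one arm, that arm's severe-toxicity percentage is reduced more, and the comparison moves in its favour. The events concerned are the asparaginase class toxicities that the plan singles out for attention.

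The SAP also gives the programmer two rules for the same kind of summary: no upper limit in 5.8.1, and an upper limit at Grade 4 in 3.5.3 and the output list.

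**Working it through.** The plan states no figure for this point, so the check is mainly of text.

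**1. Where a fatal (Grade 5) event falls**

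| Place | Rule | Grade 5 included? |
|---|---|---|
| Protocol 4.3.2 and SAP 3.5.3, named toxicities | Grade 3 or 4 | No |
| Same sections, other non-hematologic | Grade 4 | No |
| Tables 14.3.1.2.3, 14.3.1.2.4, 14.3.1.2.8 | Grade 3 or 4 | No |
| SAP 5.8.1 shell, maximum-grade rows | Grades 1 to 4 | No |
| SAP 5.8.1 shell, fatal rows (pancreatic and diabetogenic only) | Fatal | Yes |
| SAP 5.8.1 summaries | Grade ≥3; AEs ending in death | Yes |
| Table 14.3.1.2.7 | All grades | Yes, but grade is not in the title |
| Tables 14.3.2.1 and 14.3.2.2 | Deaths | Yes, but not by toxicity |

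No AE table listed in SAP 8.1 is titled Grade ≥3, so the 5.8.1 rule has no matching output there.

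**2. Whether a lower-grade record would rescue the count.** Protocol 11.1.2.2 says that when several events and symptoms belong to one main AE, only the main AE is recorded. A fatal pancreatitis or hepatic failure may therefore be a single Grade 5 record, with no separate Grade 3 or 4 record for that patient.

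**3. Which toxicities are most exposed.** Pancreatic and diabetogenic events have a dedicated table by arm with fatal rows. Hepatic, allergic and coagulation events do not. Their only listed special-interest output by grade is Table 14.3.1.2.8.

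**4. Effect on the comparison.** In each arm let p be the proportion of patients with a qualifying event of Grade 3 or higher, and f the share of those patients whose only qualifying record is Grade 5. The plan's count gives p × (1 − f). The reported ratio, arm B to arm A, is the full ratio multiplied by (1 − f_B)/(1 − f_A). It is unchanged only if f_A = f_B. The documents give neither f.

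**5. Illustration of size.** Assume a fatal special-interest toxicity rate r in the 82 arm B patients. Expected number = 82 × r; chance of at least one = 1 − (1 − r)^82.

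- r = 1%: 82 × 0.01 = 0.82 patients; chance 0.561
- r = 2%: 82 × 0.02 = 1.64 patients; chance 0.809
- r = 5%: 82 × 0.05 = 4.1 patients; chance 0.985

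These rates are assumptions, not figures from the plan.

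**6. Limiting toxicity.** SAP 3.1 states no relatedness condition and adds a treatment-change clause. Protocol 8.11 requires relatedness to GRASPA, gives examples rather than a closed list, and has no such clause. Protocol 11.6 points to stopping rules, and no section of that name appears in the supplied protocol.

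**The case against.** The strongest reply is that fatal AEs are fully reported. SAP 5.8.1 summarises them by arm within Grade ≥3 and as AEs ending in death, and describes each one individually. They also appear among the serious AEs, in Table 14.3.1.2.7 and in the deaths outputs. This stands. A reader might infer that fatal toxicity goes uncounted, and the documents do not support that.

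Second, protocol 4.3.2 and SAP 3.5.3 introduce their lists as matters for specific attention within a full safety assessment, not as an exclusive counting rule. The table titles are only an index, because SAP 1 places the output shells in a separate document. This softens the point but does not remove it: the titles and the 5.8.1 shell are the only output instructions supplied, and they conflict with the Grade ≥3 text.

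Third, a reader might infer that the two documents would produce different limiting-toxicity counts. That goes too far. Protocol 8.11 governs when an individual patient stops treatment. SAP 3.1 describes an IDMC review already held, no output in SAP 8.1 or 8.2 tabulates limiting toxicities, and the IDMC charter is not supplied. What remains is three texts that do not agree.

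**Conclusion.** The point holds as an internal inconsistency that affects the result of a named comparison. Read literally, the severe special-interest comparison by arm leaves out its worst outcome, most clearly for hepatic, allergic and coagulation events. The overall safety report does not leave it out.

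The size is unknown. The 0.8 to 4.1 patients above rest on an assumed 1% to 5% rate, and on those patients having no separate Grade 3 or 4 qualifying record. A reader might be tempted by a wider range covering any fatal non-hematologic AE, such as 5% to 20% (82 × 0.05 = 4.1 to 82 × 0.20 = 16.4 patients). Nothing in the documents supports that range. The direction of any distortion between arms is also unknown.

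The limit originates in the protocol and is carried into SAP 3.5.3. The conflict with Grade ≥3 lies within the SAP.

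**What to change.** For reporting only:

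- In SAP 3.5.3 and the matching protocol 4.3.2 endpoints, replace Grade 3 or 4 with Grade ≥3, and Grade 4 with Grade ≥4.
- Retitle Tables 14.3.1.2.3, 14.3.1.2.4 and 14.3.1.2.8 to Grade ≥3, so that they match SAP 5.8.1.
- Add a Grade 5 row to the maximum-grade block of the SAP 5.8.1 shell.

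Separately, reconcile SAP 3.1, protocol 8.11 and protocol 11.6 on limiting toxicity (relatedness, the treatment-change clause, and where the stopping rules are set out). This review takes no position on which clinical rule is right and proposes no threshold for it.

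The cost is wording, table titles and one shell row, including a wording change to the protocol. No new data are needed. The downside is that reported severe-toxicity percentages may be slightly higher.
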